Description: A simulated strategy where patients receive no magnesium supplementation throughout the 28-day follow-up, regardless of serum magnesium levels.

Group 2: Always Treat Strategy

Description: A simulated strategy where patients receive daily magnesium supplementation throughout the 28-day follow-up.

Group 3: Dynamic Treat Strategy

Description: A simulated strategy where magnesium supplementation is administered on a given day only if the daily serum magnesium level falls below 1.7 mg/dL.

Reference: Natural Clinical Course (Observed data).

6. Eligibility Criteria

Study Population: Adult patients admitted to the ICU in the MIMIC-IV database (2008-2019).

Inclusion Criteria:

1. Age \geq 18 years.
2. Admitted to the Intensive Care Unit (ICU).
3. Developed hypomagnesemia (Serum Magnesium < 1.7 mg/dL) within the first 72 hours of ICU admission.

Exclusion Criteria:

1. Admitted due to cardiac or cardiosurgical causes (e.g., Cardiac Surgery Recovery Unit, CCU, CVICU).
2. Underwent cardiac surgery during hospitalization (identified by ICD-9/10 procedure codes).
3. Primary discharge diagnosis of major cardiac conditions (e.g., myocardial infarction, heart failure, arrhythmias).

7. Outcome Measures

Primary Outcome Measure:

1. 28-Day All-Cause Mortality

Description: Cumulative incidence of death from any cause within 28 days from inclusion (Time Zero).

Time Frame: 28 days.

Secondary Outcome Measures:

1. Risk Difference (RD)

Description: The absolute difference in mortality risk between the emulated strategies (Never/Always/Dynamic) and the natural clinical course or between strategies.

Time Frame: 28 days.

2. Number Needed to Treat (NNT)

Description: Calculated to estimate the number of patients needed to be managed under a specific strategy to avert one death.

Time Frame: 28 days.

SECTION 2: STATISTICAL ANALYSIS PLAN (SAP)

1. Analysis Dataset

Source: MIMIC-IV database (version 3.1).

Data Structure: Longitudinal dataset with a daily time-grid (days 0 to 27) relative to Time Zero (T0).

Missing Data Handling: Last Observation Carried Forward (LOCF) will be used for time-varying covariates.

2. Variables

Exposure (Treatment): Magnesium replacement therapy (binary variable per day: administered yes/no).

Baseline Covariates: Age, Gender, Charlson Comorbidity Index (CCI).

Time-Varying Covariates (Daily):

Laboratory: Serum magnesium, Hemoglobin, Creatinine, Arterial pH.

Vitals/Scores: Mean Blood Pressure (MBP), SOFA score.

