Therapeutics: Vasopressor use (binary).

Outcome: Death (binary).

Competing Event: Live discharge from ICU.

3. Statistical Methodology: The G-Formula

To estimate the causal effect of dynamic magnesium strategies while accounting for time-varying confounding affected by prior treatment (feedback loops), the parametric G-formula will be employed.

Step 1: Parametric Modeling

Pooled parametric regression models will be fitted for:

- The outcome (Death).
- The competing event (Live discharge).
- Each time-varying covariate (Mg, Hb, Cr, pH, MBP, SOFA, Vasopressors).

Model Specifications: Models will include lagged values, cumulative averages, and non-linear quadratic terms for continuous variables to capture complex dependencies. An interaction term between Magnesium Treatment and SOFA score will be included.

Step 2: Monte Carlo Simulation

A random sample of 5,000 subjects (bootstrapped) will be used for simulation.

We will simulate the 28-day trajectory of the cohort under the three specific interventions (Never Treat, Always Treat, Dynamic Treat) by setting the treatment variable according to the rule of each strategy and predicting subsequent covariates and outcomes based on the fitted models.

Step 3: Effect Estimation

Cumulative Risk: Calculated for mortality at Day 28 for each strategy.

Comparisons: Risk Difference (RD) and Risk Ratio (RR) will be calculated comparing 'Always Treat' and 'Dynamic Treat' against 'Never Treat' (Reference).

Inference: 95% Confidence Intervals (CIs) will be derived using non-parametric bootstrapping with 1,000 resamples.

4. Sensitivity Analyses

To verify the robustness of the G-formula models, the following analyses will be performed:

1. Simplified Models: Re-running the analysis using linear models for all covariates (excluding quadratic terms).
2. No Interaction Models: Re-running the analysis excluding the treatment-by-SOFA score interaction term.
3. E-value Calculation: To assess the potential impact of unmeasured confounding on the observed Risk Ratio.

5. Subgroup Analyses

Treatment effects will be evaluated across the following baseline subgroups:

1. Hypomagnesemia Severity: Severe vs. Mild (dichotomized by median).
2. Renal Function: Creatinine ≥ 1.2 vs. < 1.2 mg/dL.
3. Hemodynamic Status: Vasopressor use vs. None.
4. SOFA Score: ≥ 8 vs. < 8 .
5. Age: ≥ 65 vs. < 65 years.

Interaction p-values between subgroups will be estimated via bootstrap-based covariance correction.

6. Software

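### Calendar period enters no model although the cohort is described as 2008-2019, so residual time trends in prescribing and mortality could bias the strategy contrasts in either direction

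*Combined protocol and SAP*

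**What the plan says.** Protocol section 6 describes the source population as "Study Population: Adult patients admitted to the ICU in the MIMIC-IV database (2008-2019"). None of the numbered inclusion or exclusion criteria refers to a year.

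SAP section 2 lists what is adjusted for:

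- Fixed at baseline: "Baseline Covariates: Age, Gender, Charlson Comorbidity Index (CCI").
- Daily: "Laboratory: Serum magnesium, Hemoglobin, Creatinine, Arterial pH"; "Vitals/Scores: Mean Blood Pressure (MBP), SOFA score"; "Therapeutics: Vasopressor use (binary").
- Exposure: "Magnesium replacement therapy (binary variable per day: administered yes/no").

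The only time axis, in SAP section 1, is a "Longitudinal dataset with a daily time-grid (days 0 to 27) relative to Time Zero (T0"). It counts days since the first low magnesium value and carries no information on when the patient was admitted.

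On functional form, SAP section 3 (Step 1) states: "Models will include lagged values, cumulative averages, and non-linear quadratic terms for continuous variables to capture complex dependencies". It adds one interaction, treatment by SOFA. The sensitivity analyses in SAP section 4 drop the quadratic terms, drop that interaction, and compute an E-value. The five subgroups in SAP section 5 are defined by magnesium, creatinine, vasopressor use, SOFA and age.

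**The concern.** SAP section 3 sets out to estimate a causal effect, and the protocol's detailed description says the results are meant to inform guidelines. The parametric g-formula supports that reading only if, given the modelled history, no unmeasured factor drives both daily treatment and death. In a cohort covering many admission years, calendar period is an obvious candidate for such a factor. Replacement practice can change, and so can survival for a patient of given measured severity.

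The listed severity measures describe the patient's state. They would block this path only so far as the drift in mortality runs through them. Period could also affect time to live discharge. The plan models discharge as a competing event, so a change there would feed into the simulated 28-day risk.

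The planned checks do not address this. Removing quadratic terms or the SOFA interaction leaves the omitted variable omitted. The E-value states how strong an unmeasured factor would have to be; it neither measures period nor adjusts for it.

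At stake are the risk differences and risk ratios against Never Treat, and the number needed to treat derived from them.

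**Working it through.** **1. Text check.** I looked for admission year or period in each place where it could enter.

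| Place | Content | Calendar period? |
|---|---|---|
| Baseline covariates | age, gender, comorbidity index | no |
| Daily covariates | Mg, Hb, creatinine, pH, blood pressure, SOFA, vasopressors | no |
| Time axis | follow-up days 0-27 | no |
| Model terms | lags, cumulative averages, quadratics, treatment × SOFA | no |
| Sensitivity analyses | linear models, no interaction, E-value | no |
| Subgroups | Mg, creatinine, vasopressors, SOFA, age | no |

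The span is 2019 − 2008 + 1 = 12 calendar years.

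**2. Illustration of size.** The documents give no sample size, treated share or mortality, so there is no figure to reproduce. All inputs here are assumptions: four equal periods, no magnesium effect in any period, a single treated/untreated comparison and no other covariates. With t the share treated and m the mortality in each period,

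- risk in treated = Σ(t·m) / Σt
- risk in untreated = Σ((1−t)·m) / Σ(1−t)

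*Either trend flat.* With t = 40% throughout and m = 18, 16.5, 15, 13.5%: treated 0.252/1.6 = 0.1575; untreated 0.378/2.4 = 0.1575; RR 1.00.

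*Weak* (t 40 to 50%, m 16 to 14%, equal steps): treated 0.2689/1.8 = 0.1494; untreated 0.3311/2.2 = 0.1505; RR 0.99.

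*Middle* (t = 30, 38, 45, 52%; m = 18, 16.5, 15, 13.5%): treated 0.2544/1.65 = 0.1542; untreated 0.3756/2.35 = 0.1598; RR 0.965; RD −0.56 percentage points. The spurious number needed to treat is about 1/0.00565 = 177.

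*Steep* (t 20 to 60%, m 20 to 12%, equal steps): treated 0.2382/1.6 = 0.1489; untreated 0.4018/2.4 = 0.1674; RR 0.889; RD −1.85 points. The spurious number needed to treat is about 1/0.0185 = 54.

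*Middle, with use falling instead* (t = 52, 45, 38, 30%; same m): treated 0.26535/1.65 = 0.1608; untreated 0.36465/2.35 = 0.1552; RR 1.036. The sign reverses and treatment looks harmful.

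Within any one period of these examples RR = 1.00 and RD = 0, by construction. Conditioning on period therefore removes the bias in the illustration.

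**3. Bound.** Suppose period is associated with treatment by a risk ratio a and with death by a risk ratio b, given the other covariates. The RR can then shift by at most a·b/(a+b−1):

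- 1.2 and 1.2: 1.44/1.4 = 1.03
- 1.5 and 1.5: 2.25/2 = 1.125
- 2.0 and 2.0: 4/3 = 1.33

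**The case against.** The strongest reply is that nothing in the documents shows a trend. Bias requires both prescribing and mortality to have moved, and to have moved after conditioning on a fairly rich daily history. If either was flat, there is none. This stands. A reader might infer from the 12-year span that secular change will be reported as a magnesium effect, and in particular as a false benefit. The documents support neither the fact of bias nor its direction.

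A reader might also infer that the bias would run the same way in every subgroup, so that the subgroup tables could not reveal it. That holds only if both trends have the same direction in each stratum, which the documents do not show.

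The illustrations are also far from the planned estimator. They ignore the covariates, daily treatment and competing discharge. The listed covariates would probably absorb part of any drift. In the other direction, a 28-day sustained strategy could accumulate bias if treatment history in the death model acts as a proxy for period; the SAP does not say whether cumulative treatment is a term. So the figures are neither an estimate nor a bound for the Always- or Dynamic-versus-Never contrasts.

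Finally, the years in protocol section 6 may only describe database coverage. The documents do not establish that an admission period is recorded for each patient, or how finely. That limits how specific the fix can be.

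None of this supplies a reason for leaving period out. The plan offers none, and the E-value does not take its place.

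**Conclusion.** The omission is real and worth correcting, as a cheap improvement rather than a demonstrated error in the result. Calendar period is absent from every specified model and check. If prescribing and mortality both drifted conditional on the listed covariates, the strategy contrasts could be biased either way. The documents do not allow the amount to be estimated. Under the stated assumptions the crude shift is nil without two trends, 1% to 3.5% in the risk ratio for weak to middle trends, and about 11% for a steep one in which use triples while mortality falls from 20% to 12%. A by-period table would show whether the concern matters here. If either trend is flat within the measured covariates, it closes.

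**What to change.** In SAP section 2, add admission period to the baseline covariates as a categorical variable, at the finest grouping the dataset provides. In SAP section 3, Step 1, carry it into the death model, the live-discharge model and each time-varying covariate model. At minimum, add a period-adjusted re-run to SAP section 4. The protocol already lists the study as completed, so label such a re-run post hoc.

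Report the share treated and 28-day mortality by period, so that readers can see whether the two move together and whether both treated and untreated days occur in every period.

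A treatment-by-period interaction is optional. It addresses whether the effect differs over time, which is a separate question from confounding, and it is not needed here.

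The cost is a few extra parameters per model, a re-run including the bootstrap, and possibly slightly wider intervals. Before committing, confirm that the analysis dataset holds a period variable for each patient.

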STUDY PROTOCOL AND STATISTICAL ANALYSIS PLAN

Official Title:

Dynamic Magnesium Replacement Strategies and 28-Day Mortality in Non-Cardiac Critically Ill Patients: A Target Trial Emulation Study

Date: December 24, 2025

Principal Investigator: [name]., Ph.D.

Study Type: Observational (Retrospective Cohort)

SECTION 1: STUDY PROTOCOL

1. Study Identification

Brief Title:

Magnesium Replacement Strategies in Non-Cardiac ICU Patients

Official Title:

Dynamic Magnesium Replacement Strategies and 28-Day Mortality in Non-Cardiac Critically Ill Patients: A Nonrandomized Clinical Trial using Target Trial Emulation

Study Design:

Observational, Retrospective, Cohort Study.

2. Study Status

Overall Status: Completed (Retrospective analysis of existing data).

Study Start Date: September 2025 (Analysis start).

Primary Completion Date: December 2025.

Study Completion Date: December 2025.

3. Study Description

Brief Summary:

This study evaluates the association between different dynamic magnesium replacement strategies and 28-day all-cause mortality in non-cardiac critically ill patients with hypomagnesemia. Using data from the MIMIC-IV database, the study employs a target trial emulation framework (G-formula) to simulate and compare three strategies: 'Never Treat', 'Always Treat', and 'Dynamic Treat' (treat only when hypomagnesemic).

Detailed Description:

Magnesium supplementation is common in the ICU, but evidence for its mortality benefit in non-cardiac patients is lacking. This study aims to fill the gap by emulating a randomized controlled trial using observational data. We utilize the Medical Information Mart for Intensive Care IV (MIMIC-IV) database. We define 'Time Zero' as the first occurrence of hypomagnesemia (<1.7 mg/dL) within 72 hours of ICU admission. We apply the parametric G-formula to adjust for time-varying confounding affected by prior treatment, a method superior to conventional regression for dynamic treatment regimes. The study aims to inform clinical guidelines regarding the necessity and safety of routine magnesium repletion.

4. Study Design

Observational Model: Cohort.

Time Perspective: Retrospective.

Target Follow-Up Duration: 28 Days.

Biospecimen Retention: None.

5. Groups / Cohorts

Since this is a target trial emulation, the "Groups" are hypothetical strategies defined by the analysis as follows:

Group 1: Never Treat Strategy

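### The daily covariates omit potassium and new arrhythmia, so confounding by these possible reasons for giving magnesium may remain beyond what the listed severity measures capture, and only an E-value addresses it

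*Combined protocol and SAP*

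**What the plan says.** The protocol's Detailed Description rests the causal claim on measured covariates: "We apply the parametric G-formula to adjust for time-varying confounding affected by prior treatment". SAP 2 (Variables) then lists what is measured.

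- Daily laboratory values: "Laboratory: Serum magnesium, Hemoglobin, Creatinine, Arterial pH".
- Daily physiology: "Vitals/Scores: Mean Blood Pressure (MBP), SOFA score".
- Daily co-treatment: "Therapeutics: Vasopressor use (binary").
- At baseline: "Baseline Covariates: Age, Gender, Charlson Comorbidity Index (CCI").
- Exposure: "Magnesium replacement therapy (binary variable per day: administered yes/no"). The reason for a dose is not recorded.

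SAP 3, Step 1 repeats the daily set as the list of models to be fitted: "Each time-varying covariate (Mg, Hb, Cr, pH, MBP, SOFA, Vasopressors"). The two lists agree, so the set reads as closed. Arrhythmia is mentioned once, in Protocol 6, exclusion 3: "Primary discharge diagnosis of major cardiac conditions (e.g., myocardial infarction, heart failure, arrhythmias"). Of the three sensitivity analyses in SAP 4, one drops the quadratic terms, one drops the treatment-by-SOFA interaction, and one computes an E-value.

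**The concern.** The parametric g-formula adjusts only for the covariates it is given. Its estimates have a causal reading if, given those covariates and past treatment, the decision to give magnesium on a day is unrelated to prognosis. A clinician may give magnesium for reasons other than the magnesium level, and a new arrhythmia and low potassium are two plausible ones. If such a prompt also carries information about death that the seven daily covariates miss, treated and untreated patient-days are not comparable.

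The arrhythmia exclusion does not settle this. It works on the primary discharge diagnosis, so a patient with another primary diagnosis who develops an arrhythmia during follow-up stays in the cohort with nothing in the data to mark it.

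The planned risk difference, risk ratio and number needed to treat are all at stake. The study aims to inform guidelines on routine repletion, where even a small spurious effect could matter.

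**Working it through.** The documents state no expected effect, event count or prescribing frequency, so there is no figure of theirs to reproduce. The check has two parts.

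**1. Reading the lists.** SAP 2, SAP 3 Step 1 and SAP 4 were compared for each candidate prompt.

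| Item | Baseline | Daily | Added in a sensitivity analysis |
|---|---|---|---|
| Potassium | no | no | no |
| Rhythm or new arrhythmia | no | no | no |
| Antiarrhythmic drug | no | no | no |
| General severity (SOFA, blood pressure, vasopressors, pH, creatinine) | – | yes | – |

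**2. Scale, under assumptions.** Every input below is assumed. For one binary prompt and no true effect of treatment, the bias factor is

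B = [1 + p1(RR − 1)] / [1 + p0(RR − 1)],

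where p1 and p0 are the shares of treated and untreated days carrying the prompt, and RR is its risk ratio for daily death. Strictly, all three should be conditional on the listed covariates. The values here make no allowance for what those covariates already explain.

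| p1 | p0 | RR | B |
|---|---|---|---|
| 10% | 8% | 1.5 | 1.05/1.04 = 1.01 |
| 15% | 8% | 1.5 | 1.075/1.04 = 1.03 |
| 20% | 8% | 2.0 | 1.20/1.08 = 1.11 |
| 25% | 8% | 2.5 | 1.375/1.12 = 1.23 |

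The direction depends on the sign of the prompt's association with death. With p1 = 20%, p0 = 8% and RR = 0.8, B = (1 − 0.04)/(1 − 0.016) = 0.96/0.984 = 0.98, and magnesium would look slightly better than it is.

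To put B on the absolute scale, suppose it multiplies the hazard on every day of Always Treat, and ignore discharge. With B = 1.11 and an assumed 28-day risk of 20% under Never Treat, the spurious risk is 1 − 0.80^1.11 = 21.9%, a difference of about 2 percentage points. For assumed risks of 10% and 30% the differences are about 1.0 and 2.7 points.

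**What the E-value would add.** E = RR + √[RR(RR − 1)], taking the reciprocal first if RR < 1. An observed RR of 1.10 gives 1.10 + √0.11 = 1.43, and 0.90 gives 1.46. For a small effect, therefore, a confounder associated with both treatment and death at about 1.4 to 1.5 could account for the result. The E-value reports that threshold and leaves the estimate as it was.

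**The case against.** The strongest reply is that the plan already measures deterioration. SOFA, mean blood pressure, vasopressor use, pH and creatinine are all modelled daily, with lagged values and cumulative averages specified. A reader might infer that every dose prompted by a worsening patient is analysed as if it had no cause. The documents do not support that: only the part of a prompt not reflected in those covariates is unadjusted. This stands, and it limits the point.

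Three further inferences also go too far.

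- **That the bias makes magnesium look harmful.** This needs the prompt to raise mortality after adjustment. It can be argued for arrhythmia, but is much less clear for low potassium.
- **That the bias sits mainly in doses given at magnesium of 1.7 mg/dL or above, and so in Always Treat.** The only treatment interaction the SAP specifies is with SOFA. Without a treatment-by-magnesium term, any bias enters a treatment effect that Dynamic Treat also uses.
- **That the bias is as large as the effect being sought.** No expected effect is stated.

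It is also fair to say that the documents never state that magnesium is given for arrhythmia or low potassium. Exclusions 1 and 2 (cardiac units, cardiac surgery) further narrow prescribing for cardiac reasons. And a same-day arrhythmia placed before treatment in the model could in fact follow the dose, so that adjusting for it would condition on a consequence of treatment. The fix has to deal with that.

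None of this supplies the missing variables.

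**Conclusion.** The point holds in a limited form. Potassium and new arrhythmia are adjusted for nowhere, the discharge-diagnosis exclusion does not capture arrhythmia arising during follow-up, and no planned analysis adds a confounder. If these prompts influence dosing and relate to death beyond the listed severity covariates, residual confounding by indication remains and the E-value does not remove it.

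Both conditions are clinical assumptions. The illustrative factor of 1.01 to 1.23 rests wholly on assumed prevalences and risk ratios, before any absorption by SOFA and vasopressors. The size and direction in this cohort cannot be determined from the documents. This is an inexpensive improvement to a study that depends entirely on adjustment for measured confounders. It does not show that the estimates are wrong.

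**What to change.** 1. In SAP 2, add daily serum potassium to the time-varying covariates, and in SAP 3 Step 1 add a model for it. Use the value measured before that day's magnesium dose or, failing that, the prior-day value.
2. In SAP 4, add a named sensitivity analysis that also includes a new-arrhythmia indicator, from charted rhythm or the start of an antiarrhythmic drug. Count it for a day only if its time stamp precedes that day's first magnesium dose, and otherwise lag it one day. Report how complete the rhythm charting is.
3. State the exchangeability assumption explicitly, naming the reasons for treatment that remain unmeasured.
4. The protocol lists the study as completed, so label these analyses post hoc if results are already known.

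Cost: extraction of one or two more variables from the same database, two more covariate models, and a re-run of the simulations with their 1,000 bootstrap resamples. Because potassium would enter the primary model, the existing sensitivity and subgroup analyses would need re-running too. Rhythm charting may prove incomplete, which is why the arrhythmia version is placed as a sensitivity analysis.

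### The primary outcome is 28-day all-cause death, but treating live ICU discharge as a competing event most naturally yields the risk of death before ICU discharge

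*Combined protocol and SAP*

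**What the plan says.** The protocol's aim (Protocol 3, Brief Summary) concerns "28-day all-cause mortality in non-cardiac critically ill patients with hypomagnesemia". Protocol 7 defines the primary measure as "Cumulative incidence of death from any cause within 28 days from inclusion (Time Zero"), with no restriction to deaths in the ICU.

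The SAP sets up the analysis as follows:

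- SAP 2, Variables: "Outcome: Death (binary"), followed by "Competing Event: Live discharge from ICU".
- SAP 3 Step 1: pooled models are fitted for death, for each time-varying covariate and for "The competing event (Live discharge").
- SAP 3 Step 2: "We will simulate the 28-day trajectory of the cohort under the three specific interventions".
- SAP 3 Step 3: "Cumulative Risk: Calculated for mortality at Day 28 for each strategy".

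SAP 1 sets a daily grid from day 0 to day 27 and uses LOCF for time-varying covariates. Neither document says whether records continue after ICU discharge, whether deaths after discharge are counted, or how daily treatment is recorded after discharge.

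**The concern.** A competing event is one after which the outcome can no longer happen. Live ICU discharge does not meet that definition for death by day 28, because a discharged patient can still die on the ward or at home. If discharge is nevertheless handled as competing, those patients leave the risk set as non-deaths, and the headline figure is ICU mortality under a 28-day all-cause label.

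The consequence goes beyond a lower absolute risk. The cumulative incidence of death before discharge depends on the discharge rate as well as the death rate. A strategy that only shortens or lengthens ICU stay can therefore change the planned risk without a matching change in 28-day mortality. The RD, RR, NNT, five subgroup analyses and E-value all inherit the mismatch. The NNT is the most exposed to misreading, since Protocol 7 expresses it in terms of deaths averted.

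**Working it through.** **No figure to reproduce.** The documents give no sample size, event count, death rate or discharge rate. The check is therefore of logic first and illustration second.

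**Step 1. What each handling of discharge would estimate.**

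| Handling of live ICU discharge | Quantity estimated | Is it 28-day all-cause mortality? |
|---|---|---|
| Competing event | Death before live ICU discharge, by day 28 | No |
| Censoring | Risk by day 28 if nobody were ever discharged | No |
| Patients stay at risk after discharge and all deaths count | 28-day all-cause mortality | Yes, but discharge is then not a competing event |

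The sensitivity analyses introduced by "To verify the robustness of the G-formula models, the following analyses will be performed" are models without quadratic terms, models without the treatment-by-SOFA interaction, and an E-value. None changes the event definition, so none would reveal the problem.

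**Step 2. Model for the illustration.** All hazards are assumed. There are 28 daily steps. In the ICU, the death hazard is hd, then the discharge hazard among that day's survivors is hc. From the day after discharge, the death hazard is hp.

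- Still in ICU at the start of day t: [(1 − hd)(1 − hc)]^t, for t = 0 to 27.
- Planned risk = sum of ICU deaths = hd × (1 − q^28)/(1 − q), with q = (1 − hd)(1 − hc).
- True 28-day mortality = ICU deaths + post-ICU deaths.
- Uncounted share = post-ICU deaths / all deaths.

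**Step 3. Level.** With hd = 2% and hc = 15%, q = 0.98 × 0.85 = 0.833 and the planned risk is 0.02 × (1 − 0.833^28)/0.167 = 11.90%.

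| hp per day | Planned risk | True 28-day mortality | Uncounted share |
|---|---|---|---|
| 0.2% | 11.90% | 15.70% | 24.2% |
| 0.4% | 11.90% | 19.33% | 38.4% |
| 0.6% | 11.90% | 22.80% | 47.8% |

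Over hd 1-3%, hc 10-20% and hp 0.2-0.6%, the uncounted share runs from 11.6% (hd 3%, hc 10%, hp 0.2%: 23.10% counted of 26.13%) to 72.1% (hd 1%, hc 20%, hp 0.6%: 4.80% of 17.18%). Placing discharge before death within the day changes the base range to 28-52% and the grid range to 13-76%.

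Handling discharge as censoring with hd = 2% gives 1 − 0.98^28 = 43.2%, which is far from any of the true values in the table.

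**Step 4. Contrast when a strategy changes only the speed of discharge.**

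| Scenario | Planned risk | True 28-day mortality |
|---|---|---|
| hd = hp = 1%, hc 10% to 20% | 8.81% to 4.80% | 24.53% in both |
| Half with hd = hp = 3%, hc 10%; half with hd = hp = 0.3%, hc 25%; both hc × 0.8 | 12.14% to 14.10% | 32.72% in both |
| hd 2%, hp 0.3%, hc 15% to 12% | RD +2.4 points, RR 1.20 | RD +1.9 points, RR 1.11 |

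In the first two rows the whole shift is spurious. The second shows that this does not require equal average hazards in and out of the ICU: they are 2.08% and 1.20% before the change, but the gap comes from patient mix rather than location. In the third row, staying longer in the ICU itself carries risk, and most of the RD is real.

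**Step 5. Contrast when a strategy changes only ICU death.** With hd 2.0% to 1.6%, hc 15% and hp 0.2-0.6%, the planned RD is −2.2 points against a true −2.0 to −2.1, and the planned RR is 0.82 against a true 0.87-0.91.

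**The case against.** The strongest reply is that the SAP never says records stop at ICU discharge. The outcome variable carries no ICU limit, the grid and simulation span 28 days, LOCF could fill in covariates, and Protocol 5 defines Never Treat and Always Treat over the full follow-up. The authors may have meant to count deaths after discharge. This is why the estimand reading is an inference. It does not rescue the text: if discharged patients remain at risk, discharge is not a competing event and should not be declared or modelled as one.

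A second reply is that the zero-effect contrasts are extreme, because each patient's death hazard is set equal in and out of the ICU. That is fair. Where the hazard truly falls on leaving the ICU, the RD distortion is modest and the RR is affected more (last row of Step 4, and Step 5). How much of a shift would be spurious depends on why hazards differ by location, which the documents do not show.

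A third is that every rate is assumed, so the percentages reflect the chosen grid. That is also true. They show that the mismatch can matter, not how large it is here. The contradiction does not depend on them.

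**Conclusion.** The concern holds and must be fixed: the stated primary outcome and the planned estimator disagree. As written, the analysis most naturally yields death before live ICU discharge. The alternative of censoring at discharge also fails to yield 28-day all-cause mortality, and nothing elsewhere in the documents resolves the conflict.

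Confidence in the contradiction is high, since it rests on the text alone. Its size and direction in these data cannot be known. Under the assumed constant hazards, roughly 12-72% of 28-day deaths would go uncounted, and the error in a contrast ranges from a few tenths of a percentage point of RD to an effect that is wholly spurious.

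**What to change.** Choose one of two routes and bring Protocol 7, SAP 2 and SAP 3 into line with it.

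**(a) If death dates after ICU discharge are available.** Keep 28-day all-cause death as primary. Remove live ICU discharge as a competing event and count every death through day 27 of the grid. State how covariates and treatment are handled after ICU discharge, including whether LOCF is meant to cover those days; treatment currently has no rule at all. Keep the present analysis as a secondary outcome labelled ICU death. The cost is the linked death dates, whose availability the documents do not show, plus a re-run that includes the 1,000 bootstrap resamples.

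**(b) If they are not.** Rename the primary outcome, titles and conclusions as ICU death by day 28 with live ICU discharge as a competing event. Report each strategy's cumulative incidence of live discharge beside it. Reconcile the Protocol 5 strategy definitions, which run for the full 28 days, with follow-up that effectively ends at discharge. Because Protocol 2 lists the study as completed, disclose the renaming as post hoc. The cost is mainly wording and one extra reported quantity, but the 28-day all-cause claim is given up.

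Neither route needs new patients.
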